## **10.4 Dose Hold and Discontinuation Criteria (2 of 3 Rule)**

When a blood pressure, heart rate, or QTcF interval value meets criteria for withholding a dose (Section 13.2.2) or discontinuation from the study (Section 13.2.3), the value needs to be confirmed by the site personnel by repeating the vital sign measurement or ECG recording, approximately 10 to 15 minutes later. If the value is confirmed by the second measurement, the appropriate action will be taken (dose hold or study discontinuation) and the confirmatory value will be recorded in the subject's source document and appropriate eCRF. If the second value does not meet the specified criteria, a third measurement will be taken approximately 10 to 15 minutes later. If this value is confirmatory, the appropriate action will be taken (dose hold or study discontinuation) and the last confirmatory value will be recorded in the subject's source document and appropriate eCRF. If the third value does not confirm the initial finding, then no action should be taken and the third value should be entered in the subject's source and appropriate eCRF. Note that should a second or third measurement be required with waiting between measurements, the timing of the

measurement will not be considered a protocol deviation (i.e., outside the protocol-specified window).

Whenever blood pressure, heart rate, or QTcF interval values meet dose hold or study discontinuation criteria, these are to be recorded on the subject's eCRF as an adverse event (AE) or serious adverse event (SAE), as applicable. Examples are:

Item	Record Adverse Event of:
Resting Vital Signs	
SBP <90 mmHg and >20% below screen value	Hypotension
DBP <50 mmHg and >20% below screen value	Hypotension
Pulse <50 bpm and >20% below screen value	Bradycardia
Orthostatic Vital Signs	
SBP >25% below recumbent values	Postural hypotension
DBP <25% below recumbent values	Postural hypotension
Pulse >25% below recumbent values	Postural bradycardia

DBP = diastolic blood pressure, SBP = systolic blood pressure

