### 13.2.3 Discontinuation Criteria

A subject will be discontinued from the study if any of the criteria listed below are met (see Section 10.4 for details on repeat confirmatory requirements). All instances should be recorded in the subject's source document and AE or SAE eCRF, as applicable.

- Resting systolic blood pressure <70 mmHg;
- Resting diastolic blood pressure <40 mmHg;
- Resting pulse <40 bpm;
- QTcF >500 msec or >25% above screen value for both males and females; or
- Syncope.

Additional discontinuation criteria based on cardiovascular events are:

- New onset of clinically significant abnormal ECG per Investigator judgment (e.g., second or third degree heart block or uncontrolled arrhythmia, prolonged QTcF interval).
- Persistent symptomatic hypotension (e.g., hypotension not responding to bed rest or fluids).
- Single occurrence of symptomatic bradycardia (as assessed by Principal Investigator/study physician/assigned staff, regardless of blood pressure) associated with chest pain, shortness of breath, or decreased level of consciousness.
- Persistent hypertension – resting blood pressure  $\geq 185/110$  mmHg recorded on 3 separate occasions taken at least 5 minutes apart AND within a 1-hour time period. If 2 of 3 readings are  $\geq 185/110$  mmHg (either systolic  $\geq 185$  mmHg or diastolic  $\geq 110$  mmHg) the subject must be discontinued.
- Medical Intervention for Cardiovascular Event: Any medical intervention (nonmedication or medication inclusive) used for the treatment of any cardiovascular event, with the exception of a positional intervention in subjects displaying hypotension.
- Any other clinically significant cardiovascular signs or symptoms that would place the subject at risk.
- Subject misses more than a total of 6 doses during Days 1-7.

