### 13.3 Treatment Compliance

All subjects will receive all 4 doses of lofexidine in a clinic setting for the first 3 days of lofexidine treatment (Days 1-3) and then, per clinical judgment of the Principal Investigator, subjects can continue to receive lofexidine doses in a clinic setting or can be treated outside of the clinic (outpatient) for the remaining 4 days of mandatory lofexidine treatment (Days 4-7). Per Principal Investigator judgment, subjects can continue lofexidine treatment beyond Day 7 on an outpatient basis only for up to an additional 7 days (Days 8-14). No subject will receive lofexidine for more than 14 days total. In an in-clinic setting, each dose will be observed by study staff and hand and mouth checks will be performed. In an

 See Section 15.5.3 for procedures for assessment of prolonged QTcF interval.

outpatient setting, self-dosing compliance will be evaluated at the next day's clinic visit by pill count, subject report of dosing in diary ([Appendix 3](#)), and a fingerprick blood sample to assess plasma lofexidine concentrations. Subjects will be instructed to call the Principal Investigator's office before taking the next dose of study medication if they notice any symptoms of hypotension and/or bradycardia (see list in Section [13.2.2](#)), especially when standing from a sitting or lying position. The study physician or assigned staff will determine if the next dose should be delayed, skipped, or the subject should be seen. Any change in prescribed dosing will be recorded and confirmed also by pill count and subject report at the next visit.

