During the treatment phase of the study, when any QTcF interval exceeds 495 msec, 2 additional ECGs should be taken at 10- to 15-minute intervals. The QTcF interval on all 3 ECGs should be confirmed by the Principal Investigator. If it is determined that 2 of the 3 QTcF intervals exceed 500 msec or >25% above screen value, then the subject will be discontinued from the study.

Any time that 2 of the 3 QTcF measurements exceed 500 msec, contact the Sponsor's Medical Safety Monitor, to discuss the subject and the AE/SAE determination.

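### The QTcF stopping rule in Protocol 13.2.3 points to two confirmatory ECG procedures with different triggers; below a screen QTcF of 396 msec, the 15.5.3 trigger lies above the 25% limit it should confirm

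*Protocol*

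**What the plan says.** Protocol 13.2.3 lists two QTcF limits for discontinuation: an absolute one at 500 msec and a relative one, "or >25% above screen value for both males and females". It gives two directions on confirming a reading. The sentence that opens the list says "see Section 10.4 for details on repeat confirmatory requirements". Footnote 1, attached to the QTcF criterion itself, refers to Section 15.5.3 "for procedures for assessment of prolonged QTcF interval".

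Protocol 10.4 applies "When a blood pressure, heart rate, or QTcF interval value meets criteria for withholding a dose" or for discontinuation under 13.2.3. In that case "the value needs to be confirmed by the site personnel by repeating the vital sign measurement or ECG recording", about 10 to 15 minutes later. A third recording is taken only if the second does not confirm. There is no minimum absolute QTcF.

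Protocol 15.5.3 says that during treatment, "when any QTcF interval exceeds 495 msec, 2 additional ECGs should be taken at 10- to 15-minute intervals". The decision rule that follows covers both limits: if "2 of the 3 QTcF intervals exceed 500 msec or >25% above screen value, then the subject will be discontinued from the study".

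SAP 6.9 (Vital Signs Measurements) tabulates subjects meeting the discontinuation criteria and repeats both QTcF limits. It mentions neither the 495 msec trigger nor whether a single reading or a confirmed one counts. The main ECG analysis is left to a separate SAP.

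**The concern.** A confirmatory step should start no later than the limit it confirms. In 15.5.3 it starts at a fixed 495 msec, whereas the relative limit moves with the subject's screen value and can lie well below that. Section 10.4 has no such floor. The protocol therefore sets two triggers for one stopping criterion and directs sites to both. I found no statement of which governs, or that they are cumulative.

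Safety is the primary objective, and some subjects take methadone or buprenorphine alongside lofexidine. Scheduled on-treatment ECGs are few: before and 3.5 hours after the first dose on Day 1, then before and 3.5 hours after the last dose. For a subject who continues treatment, an unconfirmed Day 1 post-dose reading may not be looked at again until the last dose, on Day 7 to 14 for completers. Whether a given tracing is confirmed, and so whether the subject stays in the study, could depend on which cross-reference the site follows.

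**Working it through.** The plan gives no derived figure on this point, so there is nothing to reproduce. The check is threshold arithmetic.

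**Inputs**
- Repeat trigger in 15.5.3: QTcF above 495 msec.
- Limits in 13.2.3 and 15.5.3: above 500 msec, or above 1.25 × s, where s is the screen QTcF.
- Repeat trigger in 10.4: any QTcF meeting a 13.2.3 criterion, that is, above the smaller of 500 and 1.25 × s.
- Eligibility ceiling for s (11.2.2, 15.5.3): 450 msec for males, 470 msec for females.

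**Crossovers**
- The relative limit equals the 15.5.3 trigger at s = 495/1.25 = 396 msec.
- The relative limit equals the absolute limit at s = 500/1.25 = 400 msec.

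| Screen s (msec) | Relative limit 1.25 × s | Gap 495 − 1.25 × s |
|---|---|---|
| 360 | 450.0 | 45.0 |
| 370 | 462.5 | 32.5 |
| 380 | 475.0 | 20.0 |
| 390 | 487.5 | 7.5 |
| 396 | 495.0 | 0 |
| 400 | 500.0 | none |
| 450 | 562.5 | none |
| 470 | 587.5 | none |

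**What each procedure asks for**
- *s below 396.* A reading above 1.25 × s and not above 495 msec needs a repeat under 10.4. It prompts none under 15.5.3. Example: s = 360 with a reading of 470. Since 470 is above 450, 10.4 requires a repeat, and a second value above 450 leads to discontinuation. Under 15.5.3 alone, 470 is below the trigger.
- *s of 400 or more.* A reading above 495 and up to 500 msec prompts two repeats under 15.5.3 but meets neither limit, so 10.4 asks for none. Example: s = 420, relative limit 525, reading 497. If both 15.5.3 repeats exceed 500, the subject is discontinued. Under 10.4 those repeats are not taken.
- *s from 396 to below 400.* The mismatch is at most 5 msec, between 495 and 500.

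**Does the relative limit still operate under 15.5.3 below 396?** Yes, in some cases. Take s = 360 and readings 497, 470 and 460. The 497 starts the repeats, none of the three exceeds 500, and all three exceed 450. Section 15.5.3 then discontinues on the relative limit alone.

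**Share of subjects with s below 396.** The documents give no QTcF distribution. Assuming a normal screen QTcF with mean 390 to 420 and SD 15 to 25 msec, truncated at 450, the share runs from about 6% (mean 420, SD 15) to about 66% (mean 390, SD 15). This is the share for whom the gap exists, not the share who would ever record a reading in it.

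**The case against.** The strongest reply is that 10.4 already closes the gap. The opening sentence of 13.2.3 sends every criterion there, and 10.4 has no 495 msec floor. Section 14.5.1 item 2 obliges the investigator to discontinue on the 13.2.3 criteria, and 14.5.2 item 1 allows discontinuation for a prolonged QTcF on judgment. Section 15.5.3 can be read as an extra, earlier alert just under 500 msec, so the two sections could be applied together.

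Much of this stands, and it rules out several stronger readings that a reader might infer:
- *That 15.5.3 permits repeats only above 495 msec, or that the sections order opposite actions.* It is silent at or below 495. It neither forbids a repeat nor tells the site to continue dosing.
- *That the relative criterion is almost never reached, or works only for screen values of 396 to 400 msec.* The first has no distribution behind it. The second fails on the 497, 470, 460 example.
- *That the different repeat sequences matter in themselves.* Once a first reading meets a criterion, stopping after a confirming second gives the same result as 2 of 3. The sequences can part only when the first reading met no criterion.
- *That sites would keep dosing.* They could, and mainly after the Day 1 post-dose tracing or the one before the last dose. After the last dose there is no dosing to continue.
- *That SAP counts would disagree by site.* SAP 6.9 uses the 13.2.3 limits without the 495 trigger and does not summarize by site.
- *That redundancy of the relative limit at screen values of 400 or more is an error.* It follows from any either/or rule.

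The reply does not remove the conflict. The footnote sits on the QTcF criterion itself and sends the site to the section with the higher trigger.

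**Conclusion.** The finding holds as an unresolved inconsistency in the current (Amendment 02) text: one QTcF stopping criterion and two confirmatory triggers. Below a screen QTcF of 396 msec, a site following footnote 1 to 15.5.3 alone could leave a reading above the relative limit unconfirmed, over a band of 45 msec at screen 360, 20 at 380 and 7.5 at 390. At 400 msec or above the mismatch runs the other way, over the 5 msec between 495 and 500. Either mismatch can change whether a subject is confirmed and discontinued.

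The bands are exact arithmetic on the stated thresholds. How many subjects would be affected cannot be said from the documents; it depends on the QTcF distributions at screening and on treatment, and on which section sites follow. A site that applies 10.4 has no gap for the relative limit.

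The arithmetic also assumes a single screen value. Screening takes duplicate ECGs at two times, so up to four readings, and the protocol does not say which is the screen value.

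**What to change.** Reconcile Protocol 10.4, 13.2.3 (including footnote 1) and 15.5.3 so that one trigger and one repeat sequence apply to both QTcF limits, and the trigger cannot lie above a limit it is meant to confirm. Define the screen value used for the percentage. State the same rule in SAP 6.9 for the discontinuation-criteria table, including whether a first or a confirmed reading counts. Which thresholds and which sequence stand is for the sponsor to decide; none is proposed here.

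The cost is a short protocol clarification, a note to sites, a sentence in the SAP, and an occasional extra repeat ECG. Below 396 msec, 10.4 already requires that repeat.

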#### 15.5.4 Clinical Laboratory Evaluations

##### 15.5.4.1 Standard Laboratory Tests

Standard clinical laboratory safety evaluations (see [Table 3](#)) will be performed for all subjects at screening, as needed at the study physician's discretion throughout the study, and at discontinuation from the study. For this multicenter study, a central laboratory will be used that is directly accredited by the College of American Pathologists (CAP) and licensed by the Clinical Laboratory Improvement Act of 1988 (CLIA); both certification and accreditation must be renewed every 2 years. The laboratory will need to provide a copy of current certification and provide the normal values for all analytes to determine the upper limit of normal (ULN).

Table 3. Hematology, Chemistry, and Urinalysis Tests

Hematology (a)	Chemistry (b)	Urinalysis
Hemoglobin	Cholesterol	Color
Hematocrit	Triglycerides	Clarity
Red blood cell (RBC) count	Sodium	pH
MCV	Potassium	Specific gravity
MCH	Chloride	Protein
MCHC	Carbon dioxide (CO 2 )	Glucose
RDW	Glucose	Ketones
White blood cell (WBC) count	Creatinine	Bilirubin
WBC differential (% and Abs)	Albumin	Nitrite
neutrophils	Total protein	Blood
lymphocytes	Calcium	Urobilinogen
monocytes	Phosphorus	WBC
eosinophils	Aspartate aminotransferase (AST)	RBC
basophils	Alanine aminotransferase (ALT)	Epithelial cells
Prothrombin time (PT)	Gamma-glutamyl transpeptidase (GGTP)	Bacteria
aPTT	Total bilirubin	Casts
Platelet Count	Lactate dehydrogenase (LDH)	Crystals
	Alkaline phosphatase	
	Blood urea nitrogen (BUN)	
	Thyroid-stimulating hormone (TSH)	
	Free thyroxine (T4)	

**Abbreviations:** Abs = absolute; aPTT = activated partial thromboplastin time; MCH = mean corpuscular hemoglobin; MCV = mean corpuscular volume; MCHC = mean corpuscular hemoglobin concentration; RDW = red blood cell distribution width

- (a) Blood will be collected in anticoagulant containing evacuated venous blood collection tubes (e.g., VacutainerTM).
- (b) Blood will be collected in serum separation evacuated venous blood collection tubes (e.g., VacutainerTM) and serum separated according to standard procedures.

#### 15.5.4.2 Infectious Disease Panel and Syphilis Tests

The infectious disease panel and syphilis tests will be assayed as a baseline procedure. Blood will be collected in serum separation evacuated venous blood collection tubes (e.g., VacutainerTM) and serum separated according to standard procedures. Qualitative analysis reporting positive/negative results will be performed for the following analytes: Hepatitis B surface antigen (HbsAg), Hepatitis B surface antibody (HBsAb), Hepatitis B core antibody (HBcAb), and Hepatitis C virus antibody (anti-HCV). A PPD skin test for tuberculosis and/or a chest x-ray will be performed on all subjects. If the PPD is positive, a chest x-ray is required to assess active tuberculosis. If the subject reports that s/he has been previously positive for the PPD test, the PPD test will not be performed and only a chest x-ray will be required. Syphilis antibody testing will be performed using an automated enzyme immunoassay (EIA). If the EIA is positive, a confirmatory rapid plasma reagent (RPR) test will be performed. If the RPR test is non-reactive, a confirmatory TPPA (treponema pallidum particle agglutination assay) test will be performed.

Any subject with active liver disease, active tuberculosis, or active syphilis (see [Table 4](#) for interpretation of the syphilis testing sequence) will not be eligible for study participation and

the subject will be referred, at subject's sole expense, for appropriate follow-up and/or treatment.

Table 4. Syphilis Testing Sequence

Subject History	Test and Result			Interpretation	Eligibility
	EIA/CIA/MFI	RPR	TPPA		
Unknown history of syphilis	Non-reactive	N/A	N/A	No serologic evidence	Meets eligibility
	Reactive	Reactive	N/A	Untreated or recently treated syphilis	Excluded
	Reactive	Non-reactive	Non-reactive	Probably false-positive screening test	Meets eligibility
	Reactive	Non-reactive	Reactive	Possible syphilis (e.g., early or latent) or previously treated	May be eligible; consult Medical Monitor
Known history of syphilis	Reactive	Non-reactive	Reactive	Past, successfully treated syphilis	Probably eligible; consult Medical Monitor

**Abbreviations:** CIA = chemiluminescence assay; EIA = enzyme immunoassay; MFI = multiplex fluorescent immunoassay; N/A = not applicable; RPR = rapid plasma reagent; TPPA = treponema pallidum particle agglutination assay

#### 15.5.4.3 Urine Toxicology Screening

A qualitative urine drug screen (UDS) will be performed at screening and Baseline (Day 1 before dosing) for all subjects, and every day during in-clinic lofexidine treatment and outpatient lofexidine treatment for the following drugs: amphetamines/methamphetamines, methylenedioxymethamphetamine, cocaine, barbiturates, opiates, benzodiazepines, cannabinoids, oxycodone, phencyclidine, methadone, and buprenorphine. The central lab will provide standard sets of UDS “dipsticks” for use across all sites.

#### 15.5.4.4 Pregnancy Test

A “dip-stick” pregnancy test designed to measure human chorionic gonadotropin will be performed on the first day of screening for all subjects, at Baseline (Day 1 before dosing), and at discontinuation from the study for all female subjects regardless of their childbearing capacity. The central lab will provide study sites with a supply of pregnancy dipsticks.

#### 15.5.4.5 Pharmacokinetic Sampling

A fingerprick blood sample will be collected concurrently with each scheduled ECG during the study.

A fingerprick blood sample will be collected during outpatient treatment when the subject reports to the clinic each day (before next scheduled dose) for analysis of plasma lofexidine concentration to monitor compliance.

### **15.5.5 Physical Examination**

A complete physical examination of the oral cavity, head, eyes, ears, nose and throat, cardiovascular system, lungs, abdomen (liver/spleen), extremities, skin, neuropsychiatric mental status and sensory/motor status, musculoskeletal system, and general appearance will be performed at screening for all subjects.

An update of the Physical Exam is required at Baseline (before dosing on Day 1) and then a complete physical examination should be performed 3 to 4 hours after the first dose on Day 1, as clinically warranted throughout the study, and at discontinuation from the study.

Height should be recorded at screening only.

### **15.5.6 Columbia Suicide Severity Rating Scale (C-SSRS)**

The C-SSRS measures both suicidal ideation and suicidal behavior and will be completed at Baseline (before dosing on Day 1), 3.5 hours after the first dose (8 AM) during in-clinic lofexidine treatment, once daily before an in-clinic dose of lofexidine during outpatient treatment or, if applicable, at discontinuation from the study. The Baseline version of the C-SSRS ([Appendix 5](#)) will be used to assess lifetime suicidality on Day 1 (before dosing). At all other protocol-specified time points, the C-SSRS – Since Last Visit version ([Appendix 6](#)) will be used to assess the subject's suicidality since the last assessment.

## **15.6 Other Assessments**

### **15.6.1 Prior Medications**

All medications taken by the subject for the 30 days before screening and during the screening period will be documented on the Prior Medication eCRF. The reported medications will be reviewed and approved by the Principal Investigator/study physician/assigned staff for entry into the study.

All opioids of abuse the subject has used will also be recorded at the screening visit.

### **15.6.2 Concomitant Medication Administration**

Concomitant medication administration will be recorded daily. All concomitant medications will be recorded in source and in the subject's Concomitant Medication eCRF along with dose, dates of administration, and reason for use.

## **16 REGULATORY AND REPORTING REQUIREMENTS**

### **16.1 Good Clinical Practices**

This study will be conducted in accordance with the most current version of the International Conference on Harmonization (ICH) Guideline for Good Clinical Practices (GCP). An Investigational Site File binder will be provided to all investigational sites with additional instruction as well as a place to store regulatory and study documents. The monitoring of the sites participating in the trial (either remote or on site) will be executed according to GCP guidelines and with a focused data review approach (Risk Based Monitoring [RBM]).

Monitors will examine subjects' study files including source documents in both the clinic files and subjects' official medical records, and will also review regulatory/essential documents such as correspondence with the IRB and the Sponsor (USWM). Areas of particular concern will be subject informed consent issues, protocol adherence, safety monitoring, IRB reviews and approvals, safety reports/regulatory forms, subject records, study drug accountability, and principal investigator supervision and involvement in the trial. Reports will be prepared following each visit and forwarded to the Sponsor's Clinical Project Manager. Monitors will also prepare follow-up letters detailing their findings and any items requiring further resolution or attention by the site. Follow-up letters will be provided to the Principal Investigator, site coordinator, and Sponsor's Clinical Project Manager.

## **16.2 FDA Forms 1572 and Financial Disclosure**

The Principal Investigator will sign a Statement of Investigator (FDA Form 1572) before initiating this study. The names of any sub-investigators must appear on this form.

The Principal Investigator and sub-investigators will also sign Financial Disclosure forms before initiating this study.

